## 1 Introduction

This study is a multi-centre, long-term, prospective, observational cohort study to be conducted in multiple countries in Europe. It constitutes a post-authorization safety study (PASS), to be conducted in compliance with Volume 9a of The Rules Governing Medicinal Products in the European Union (Guidelines on Pharmacovigilance of Medical Products for Human Use). Prostate cancer patients will enter the study after they begin treatment with androgen ablation therapy and will be followed for up to 5 years. Follow-up information will be collected every 3 months for the first 2 years and then every six months for the remaining 3 years or until patient discontinuation. There are no prescheduled visit regimens associated with the study. The visits in general should be part of routine clinical care and the information included into the study should also be part of the routine medical assessment. No procedures or examinations (e.g., physical exam, DEXA bone scan) are required as part of the study. Baseline data will be collected at a routine outpatient visit, follow-up data will be collected at the time of routine office visits or by telephone interviews at the approximate 3-month and 6-month time points.

All reasonable efforts and methods to minimize loss to follow-up will be undertaken to retain patients for the entire 5 years of observation, or until early discontinuation. This Observational study will enrol 1,000 patients treated with Firmagon. In addition, a comparator group of 500 patients treated with any GnRH agonist will also be enrolled. The primary aim of the study is to better understand the safety profile of Firmagon; however, inclusion of a comparator arm will provide the ability to understand the results in the more general context of androgen ablation and underlying PCa. Study enrolment will be monitored and enrolment of the control group will be locked once the target number of patients has been enrolled.

This document describes in details the planned statistical analyses for the FE200486 CS39 study protocol. The original protocol was dated on 25 Nov 2009.

### 1.1 Definitions of Terms and Abbreviations

#### 1.1.1 Definition of Terms

Terms	Definitions
Enrolled	Patient who has signed informed consent
Month	28 days / 4 weeks
Screened	Patient who enters the screening phase

## 1.1.2 Abbreviations

Abbreviations	Meaning of abbreviations in document
AE	Adverse Event
AESI	Adverse Event of Special Interest
ADR	Adverse Drug Reaction
ADT	Androgen Deprivation Therapy
ALT	Alanine aminotransferase
CI	Confidence Interval
CTCAE	Common Terminology Criteria for Adverse Events
CV	Cardiovascular
CVD	Cardiovascular Disease
ECG	Electrocardiogram
ECOG	Eastern Cooperative Oncology Group
EOt	End of Trial
GGT	Gamma-glutamyl transferase
GnRH	Gonadotropin-Releasing Hormone
IC	Informed Consent
ITT	Intention-to-treat
KM	Kaplan-Meier
LOCF	Last Observation Carried Forward
mL	Millilitre
MedDRA	Medical Dictionary for Regulatory Activities
NCI	National Cancer Institute
OC	Observed Case
PCa	Prostate Cancer
PP	Per-Protocol
PSA	Prostate-Specific Antigen
PT	Preferred Term
IRR	Incidence Rate Ratio
SAE	Serious Adverse Event
SD	Standard Deviation
SMQ	Standardised MedDRA Query
SOC	System Organ Class
TE	Treatment Emergent
TEAE	Treatment Emergent Adverse Event
TNM	Tumor, Nodule, and Metastatic
ULN	Upper Level of Normal Range

## 2 Study Objectives and Endpoints

### 2.1 Objectives

#### Primary Objective

The primary objective of this observational study is to describe the risk of the following Adverse Event of Special Interest (AESI) in association with Firmagon treatment:

- Cardiovascular events
- Events related to decreased bone density, including new onset or progression of osteoporosis or osteopenia, and fractures
- New onset or exacerbation of glucose intolerance or type 2 diabetes mellitus
- Changes in hepatic enzyme levels

#### Secondary Objectives

The secondary objectives of this Observational study are to:

- Compare the relative risks of the AESI in those patients treated with Firmagon and those treated with a GnRH agonist
- Identify any new potentially unrecognized adverse drug reactions (ADRs) by collecting adverse events (AEs) in this population
- Describe the long-term clinical evolution of PCa in patients treated with Firmagon
- Describe the all-cause mortality in patients treated with Firmagon

### 2.2 Endpoints

#### Safety Endpoints

The following endpoints will be analysed in the study:

1. Rate of AESI
  - a. Incidence rate of cardiovascular events
  - b. Incidence rate of bone fracture, including osteoporotic/fragility fractures
  - c. Incidence rate of new onset or worsening osteoporosis or osteopenia

- d. Incidence rate of new-onset diabetes mellitus
  - e. Incidence rate of all-cause mortality
2. Occurrence of relevant laboratory value changes
- a. Changes in hepatic enzymes, fasting serum glucose, testosterone and PSA levels
  - b. Incidence rate of glucose intolerance

#### 3.1 Schedule of Assessments

Patients will be enrolled after the initial decision (by the investigator) has been made to introduce Firmagon or GnRH agonist as per label indication for prostate cancer. Data will be collected at baseline and every 3 months ( $\pm$  4 weeks) for the first 2 years, then every 6 months ( $\pm$  6 weeks) for the remaining 3 years. Firmagon is dosed monthly, while GnRH agonists may be administered less frequently, therefore suggested data collection time points *may not always* coincide with treatment-related clinical visits. If necessary, telephone outreach may be used by sites to collect relevant data. Patients who discontinue ADT therapy will continue to be followed for safety outcomes in order to assess the long term safety associated with ADT.

A flowchart of *recommended* study assessments is provided in [Table 1](#).

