### 8.1 Exposure Periods

In order to limit bias from different treatment effects and overlapping treatment periods on reported adverse events, and to make data comparable to a greater degree, the total exposure period will be partitioned as follows.

At the Baseline Visit patients will be asked if they are on ADT and if so, when it was initiated. The date of Informed Consent is also recorded as part of the eCRF data collection. Start date of *main treatment period* will be considered to be the date at which both the informed consent has been signed, and the first dose has been administered. End date of main treatment period will be recorded as date of loss to follow-up, change in ADT, discontinuation of ADT, or end-of-trial visit, whatever comes first. If treatment continues after end of main treatment period (e.g. due to regimen change), a consecutive treatment period will be considered to be started. Consecutive treatment periods have a similar definition of end-of treatment period as the main treatment period.

In the case that the informed consent was not signed at time of first dosing, a “pre-consent period” is considered. This period ends when the informed consent is signed, at which time the “Main Treatment Period” starts, see Table 4.

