### **10.2 Definition of Treatment-Emergent Adverse Events**

All adverse events of exposed patients occurring during the “Main Treatment Period” or thereafter (as defined in Section 8) will be considered as treatment-emergent (TE).

Adverse events that occur before first dose (on non-exposed patients) are not defined as treatment emergent and will not be reported.

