## 10.4 Adverse Events of Special Interest (AESI)

An AESI is a subgroup of general TEAEs and as such are classified and treated as described in Section 10.3.

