### 10.4.1 Definition

The main objective of this observational study is to collect information on AESI. Specifically: cardiovascular events; new onset of diabetes mellitus; progression of osteoporosis or osteopenia; events associated with bone fractures (osteonecrosis); and all-cause mortality. The worsening of glucose intolerance based on lab data has been described in Section 9.1.5. Only events classified as serious will be considered.

Any AESI in the medical history occurring during the “Main Treatment Period” (or thereafter), or any adverse event of special interest in the adverse event report log occurring during the “Pre-consent Period” will be listed, as these possibly should be shifted from medical history to adverse event (or opposite).

In order to limit bias from different treatment effects and overlapping treatment periods and to make data comparable to a greater degree *only* AEs reported during the “Main Treatment Period” are considered (see Section 8.1 for details).

The AEs will be coded using MedDRA lowest level term (LLT). An AE included in any of the following Standardised MedDRA queries (SMQs), at the narrow search scope level, is defined as an event of special interest:

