### **10.4.2 Incidence of Adverse Events of Special Interest**

A summary table will be prepared for the incidence of each AESI. For example, for cardiovascular events, the first AE in the class of the CV SMQs will be accounted for, while the other events will be disregarded. For the incidence rate, it will be the time to this event that is used. Should no event occur, patient is lost to follow-up, or completes the trial (without an event) it is the total observed exposure time that is used, while the patient does not contribute to the derived endpoint count.

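### No AESI analysis is explicitly planned on follow-up after ADT is changed or stopped, although Section 3.1 continues that follow-up to assess long-term safety

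*SAP*

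**What the plan says.** Section 3.1 gives a purpose for following patients beyond the end of treatment: "Patients who discontinue ADT therapy will continue to be followed for safety outcomes in order to assess the long term safety associated with ADT".

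The AESI analyses use a narrower window. Section 10.4.1 says that only "AEs reported during the “Main Treatment Period” are considered", and Section 8.1 defines when that period closes: "End date of main treatment period will be recorded as date of loss to follow-up, change in ADT, discontinuation of ADT, or end-of-trial visit", taking the earliest. Table 4 shows a change of treatment regimen as the point where the main period ends. Section 8 expects such changes and gives a move from continuous to intermittent treatment as an example.

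Other sections point to a wider window. Section 10.2 counts as treatment-emergent "All adverse events of exposed patients occurring during the “Main Treatment Period” or thereafter". Section 10.4 states: "An AESI is a subgroup of general TEAEs and as such are classified and treated as described in Section 10.3". For patients without an event, Section 10.4.2 says "it is the total observed exposure time that is used" and does not mention a cut at ADT change. Section 10.5.2 names only loss to follow-up as a reason for censoring.

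Section 10.5.1 then bases its reading of increased or decreased risk on one incidence rate ratio (IRR) and its 95% confidence interval. Section 6 says that all analyses follow the treatment actually received.

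**The concern.** The AESIs are the subject of the primary objective, and follow-up after ADT ends is collected so that long-term safety can be judged. If AESIs are counted only until the first change or stop, the data gathered for that purpose support no grouped AESI rate, adjusted IRR, Kaplan-Meier curve or hazard ratio.

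Two things are at stake. The first is the question answered: the plan would describe AESI risk while patients stay on their initial ADT, but not risk over the whole follow-up. Section 3.2 itself expects higher fracture rates in longer observation. The second is robustness. Leaving the main period may be related to emerging toxicity or progression, although the SAP does not say how often or why it happens. If it is related, an event soon after the change is lost selectively. With a single window, nobody can tell whether the Section 10.5.1 conclusion depends on the cut-off.

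**Working it through.** **1. Which planned analyses use time after ADT change or stop?**

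- AESI incidence, Poisson, Kaplan-Meier and Cox analyses (10.4.2, 10.5.1 to 10.5.3): the event window is the main period, by 10.4.1. No version on all follow-up is named, not even as a sensitivity analysis.
- General treatment-emergent tables (10.1.1, 10.2, 10.3): later events are included, with person-years, rates, 95% confidence intervals and a between-group test. They are tabulated by organ class and preferred term, without adjustment.
- Tables of events generating an AESI (10.4.3, 10.4.4): described as treatment-emergent, so it is unclear whether 10.2 or 10.4.1 governs.
- All-cause mortality: 10.4.1 lists it among the AESIs but limits adverse events, and 10.6 notes that death is not itself an adverse event. The window is unclear.
- Section 10.6 endpoints: Poisson, Kaplan-Meier and Cox analyses are planned and no window is restated.

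**2. Person-time behind Table 2**

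Inputs from Section 3.2: 1,000 Firmagon patients, 5 years, 10% dropout with uniform timing (mean 2.5 years for a dropout).

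Person-years = 1000 × (0.9 × 5 + 0.1 × 2.5) = 4,750.

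Exact Poisson limits with d = rate × 47.5 events and T = 47.5 hundred person-years: lower = χ²(0.025; 2d)/(2T), upper = χ²(0.975; 2d + 2)/(2T).

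- Rate 10.00: 9.12 to 10.94, width 1.82 (Table 2: 9.14 to 10.91, 1.77)
- Rate 5.00: 4.38 to 5.68, width 1.29 (Table 2: 4.38 to 5.68, 1.30)
- Rate 0.60: 0.40 to 0.86, width 0.46 (Table 2: 0.40 to 0.87, 0.47)

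All eight rows agree within 0.03 on each limit and about 3% on width. The match is approximate: the person-years that would reproduce each printed width exactly run from 4,537 to 5,020. The stated inputs allow for dropout but not for ADT change or stop.

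**3. Share of follow-up outside the window**

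The SAP gives no frequency of change or stop, so the hazards h below are assumptions. Ignoring death and dropout, mean time in the main period over 5 years is (1 − e^(−5h))/h.

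- h = 0.1: 0.393/0.1 = 3.93 years; 1 − 3.93/5 = 21% outside
- h = 0.2: 0.632/0.2 = 3.16 years; 37% outside
- h = 0.3: 0.777/0.3 = 2.59 years; 48% outside

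**4. Effect on precision, with the 10% dropout kept**

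Person-years = 1000 × ∫₀⁵ (1 − 0.02t) e^(−ht) dt. Here the assumption is an annual proportion p leaving the main period, with h = −ln(1 − p). Interval widths are for a rate of 5 per 100 person-years.

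- No change or stop: 4,750 person-years; width 1.29; years 2 to 5 contribute 2,790
- p = 5%: 4,199 (88%); width 1.38; years 2 to 5: 2,336 (84%)
- p = 10%: 3,709 (78%); width 1.47; years 2 to 5: 1,941 (70%)
- p = 20%: 2,890 (61%); width 1.67; years 2 to 5: 1,306 (47%)
- p = 30%: 2,249 (47%); width 1.90; years 2 to 5: 844 (30%)

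The proportional loss is greatest in the later years.

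**The case against.** The restriction is deliberate. Sections 8.1 and 10.4.1 explain that it limits bias from overlapping treatments, and the primary objective concerns risk in association with Firmagon treatment. That stands, and it is why the main-period analysis should remain primary. The rationale is weakest for patients who stop ADT altogether, or who change regimen on the same drug, because no second drug overlaps.

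A reader might infer that long-term risk is never estimated, or that every later AESI is discarded. The SAP does not support either. Patients who stay on their initial ADT contribute AESI time for up to five years, and later events do reach the general tables with rates, intervals and tests. For mortality and Section 10.6 the window is unstated rather than cut.

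A reader might also infer that the cut-off removes a period of continuing drug action whose length differs by arm, since Section 3.1 says: "Firmagon is dosed monthly, while GnRH agonists may be administered less frequently". That sentence explains the timing of data collection. The SAP gives no duration of action and does not say how discontinuation is dated, so neither the existence nor the length of such a period can be established.

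Finally, attributing all follow-up to the initial drug departs from the received-treatment rule in Section 6. This is a fair objection; the departure has to be declared.

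**Conclusion.** The point holds in a limited form. Follow-up after ADT ends is collected for long-term safety, but no grouped or adjusted AESI analysis is explicitly planned on it, and the sections that define the window do not agree. Two things are missing: AESI risk that includes time after change or stop, and a check that the IRR conclusion does not rest on the cut-off.

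The size is unknown from the SAP. Under assumed constant annual hazards of 0.1 to 0.3, about 21% to 48% of a five-year follow-up lies outside the window. This is a share of person-time. Because only first events count, the share of AESIs lost need not be the same. The precision in Table 2 is optimistic for the main-period analysis to whatever extent patients change or stop ADT. That the cut-off is informative is a possibility, not something the SAP shows.

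**What to change.** - Keep the Main Treatment Period analysis as primary. Label it on-treatment, and cut events and person-time at the same date, the end of that period.
- Add to Sections 10.5.1 to 10.5.3 one prespecified secondary analysis of each AESI and of all-cause mortality over all observed follow-up, to death, loss to follow-up or end of trial, grouped by initial drug. State it as an exception to the received-treatment rule in Section 6.
- Report the secondary IRR beside the primary one.
- State which window applies to all-cause mortality and to the Section 10.6 endpoints.
- Reconcile Sections 8.1, 10.2, 10.4, 10.4.1, 10.4.2 and 10.5.2 so that event window, denominator and censoring agree.

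The cost is SAP wording and repeat runs of models already planned, on data already collected. The drawback is that exposure is mixed after a switch of drug, which is why the added analysis is secondary.

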**Table 1 Study Flow Chart**

Visit	Baseline	Follow-up	
Time	0	0-2 years (3 months ( $\pm$ 4 weeks) between the visits)	2-5 years (6 months ( $\pm$ 6 weeks) between the visits)
Informed consent (a)	x		
Inclusion/exclusion criteria	x		
Demographics	x		
History/stage/histology of PCa	x	x	x
Body weight, height and waist circumference	x	x (b)	x (b)
Medical History	x		
Concomitant medications	x	x	x
Adverse events		x	x
ADT treatment		x	x
Fasting glucose, hepatic enzymes, DEXA bone scan	x (c)	x (c)	x (c)
PSA, testosterone	x (c)	x (c)	x (c)

- a) Written informed consent must be obtained prior to any study related data collection
- b) Height, weight, and waist circumference (waist circumference only if measured) should be collected at baseline and annually thereafter
- c) At the discretion of the treating physician, estimated to be every 3 – 6 months.

Since no visits are mandated or prescheduled as part of the study, but collected at visits scheduled as a part of routine care, the changes in hepatic enzymes, fasting serum glucose, testosterone and PSA levels, will be presented by visit intervals as dictated in Section 9.1.1. The reporting date of adverse events will not be changed.

### 3.2 Study Sample Size

In a pivotal one-year Phase 3 study (Ferring Clinical Study FE200486 CS21), a serious cardiovascular event rate for Firmagon of 5 per 100 patient-years was observed in the sub-group of patients with locally advanced or metastatic PCa. In the same study, in patients treated with the GnRH agonist (leuprolide) a serious cardiovascular event rate of 8 per 100 patient-years was observed. Based on SEER database in over 22,000 PCa patients treated with GnRH agonists the expected incidence rate is approximately 10 per 100 patient years [1]. In an observational study of 73,000 Medicare enrollees with locoregional PCa, Keating et al. [2] found incidence rates of 7.23, 1.29, and 1.35 respectively for coronary heart disease, sudden cardiac death, and myocardial infarction in patients treated with GnRH agonists. Keating et al additionally showed an incident rate for new onset diabetes of 2.90 in GnRH agonist treated patients.

In the CS21 study, a bone fracture rate of 0.6 per 100 patient years for patients treated with Firmagon vs. 2.2 per 100 patient years for patients treated with leuprolide was observed in the sub-group of patients with locally advanced or metastatic PCa. However, CS21 was a one-year study, and annual fracture rates increase with age and also with an increased number of doses of GnRH agonist [3]. Therefore, the incidence rates in a longer-term observational study are anticipated to be higher. Smith et al [4] report a fracture rate of 7.91 per 100 person-years in 3,779 men with PCa (all stages) who received GnRH agonist treatment during a 5-year observation period.

With the expected incidence rates for cardiovascular events, diabetes and fracture as indicated above, 1,000 patients on Firmagon, and 500 on GnRH agonist treatment for a 5-year follow-up study and assuming a dropout rate of 10% over the course of 5 years, and a uniform distribution for the time to dropout, the 95% confidence interval for estimating the incidence rates are listed in Table 2 below (please note that the confidence interval for the smaller comparator group will be wider). These confidence intervals show the precision for estimating the incidence rates if the observed incidence rates are the same as reported in literature. The width of the 95% confidence interval is also listed in the table. The calculation was performed in STATA 11 (College Station, TX).

**Table 2 Incidence Rates for Cardiovascular Events and Fracture Reported in Literature, and the 95% Confidence Intervals the Study is Anticipated to Obtain Based on 1000 Patients on Firmagon and a Follow-up of 5 Years.**

Event	Source	Incidence rate (per 100 patient years on Firmagon)	95% Confidence Interval	Width of the 95% confidence interval
Cardiovascular events	SEER data	10.00*	9.14, 10.91	1.77
	CS21	5.00	4.38, 5.68	1.30
Coronary heart disease	Keating et al.	7.23*	6.48, 8.02	1.54
Sudden cardiac death	Keating et al.	1.29*	0.98, 1.66	0.68
Myocardial infarction	Keating et al.	1.35*	1.04, 1.74	0.70
Fractures	Smith et al.	7.91*	7.14, 8.74	1.60
	CS21	0.60	0.40, 0.87	0.47
New-onset diabetes	Keating et al.	2.90*	2.44, 3.45	1.01

\*Incidence rate for GnRH agonist, assumed to be same with Firmagon

Based on the estimates and 95% Confidence Intervals widths described above, the planned sample size (with 1000 patients enrolled on Firmagon) is considered sufficient to address the objectives of this Observational study, with reasonable precision.

#### **4 Patient Disposition**

All patients screened will be accounted for. All post-treatment allocation discontinuations (withdrawals) will be summarised by duration of study participation and main reason for discontinuation. All major protocol violations and withdrawals from trial will be summarised with frequency and percentage for each category of protocol violation or study discontinuation. The number of patients that were screened, already undergoing treatment when enrolled into the study, completed the trial, withdrew from trial will be summarised. Furthermore, the disposition/attendance of patients by visit-intervals will be provided. The number of patients screened but not allocated to treatment will be presented with the reason(s) for screen failure in a data listing.

In addition, the disposition of patients will be summarised with frequency and percentages after each follow-up visit (3 months interval for first 2 years and 6 months interval remaining 3 years).

Discontinuation rates will be estimated using the Kaplan-Meier (KM) method on time to discontinuation from date of enrolment, and graphically represented in corresponding 1-KM curves, differentiated for reason of discontinuation via cumulative incidence functions. Differences in discontinuation rates will be tested using the Log Rank test ( $\alpha=0.05$ , two-sided).

